provides a z-score indicating the likelihood of random occurrence of an observation. Together, these significant co-occurrences, or “patterns”, (i.e., those not occurring due to chance or noise) will provide a model of the data that can be used to predict treatment response trajectories. We will follow recommended nested cross-validation which validates patterns by examining the pattern discovery across a set of cross-validation trials. Participant data will be allocated in round-robin fashion into N sets. We will use 10-fold cross-validation such that a “fold” is created by using one set only for testing, and dividing the remaining between training and parameter validation. This allows unseen validation data to determine the efficacy of the discovered patterns obtained from the “training” sets and allows detection of overfitting using the validation sets. This process is then repeated whereby each fold is used only once for model testing, which will also allow us to assess the stability of the patterns discovered across the collection of training and validation exercises. Overfitting of the process is properly managed through this cross-validation strategy. In addition, we have addressed overfitting by employing association mining (versus, for example, convolutional neural networks) because it is associated with a much lower risk of overfitting (Hamilton-Wright & Stashuk, 2009) and provides a simple statistical measure of rule significance. To establish the power of these patterns, we will use information theory to score each one, describing how much support each pattern has within the overall distribution of the data. This allows us to distinguish patterns based on richly described regions of the data distribution from those with sparse support. The result is a confidence value associated with assertions made about treatment response using the patterns, indicating whether there is high confidence (based on well characterized regions of the data) or poor confidence (based on rare or conflicting regions of the data). Altogether, significant and meaningful rules and associated confidences are assembled into a rule-based framework that will allow characterizations (i.e., predictions) to be made, in new cases, describing the likely treatment response trajectory based on emotion regulation indicators. As one example, the algorithm could reveal that when child arousal (i.e., skin conductance level) is above a certain threshold, treatment response is slow, and that the framework’s confidence in this characterization is 90%. Such a result would suggest that child arousal, when above a certain threshold, is a key regulation component in treatment response, that there is a high amount of evidence within the system for this characterization, and that it would be worthwhile to consider when tailoring psychotherapy. The resulting set of significant and meaningful association rules, or algorithms, will be applied to a predictor system,⁸⁰ which will form the basis of bidirectional and iterative conversations with KT users and partners about applying the algorithms to a clinical decision-making framework.

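### Aim 2 counts rediscovery of a pattern across ten overlapping cross-validation trials as validation and stability, although such recurrence is not independent replication

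*Protocol*

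**What the plan says.** The point concerns the Aim 2 machine-learning text in the Protocol's Data Analysis section. Candidate patterns are scored by a Haberman residual, read as a z-score. The cross-validation then works as follows.

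- **Partition.** "Participant data will be allocated in round-robin fashion into N sets". There are ten folds, each made by "using one set only for testing, and dividing the remaining between training and parameter validation". The proportion given to training is not stated.
- **Validation by rediscovery.** The procedure "validates patterns by examining the pattern discovery across a set of cross-validation trials".
- **Held-out check.** "This allows unseen validation data to determine the efficacy of the discovered patterns", and "each fold is used only once for model testing".
- **Stability.** The repetition over folds is a step "which will also allow us to assess the stability of the patterns discovered across the collection of training and validation exercises".

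The text concludes that cross-validation deals with overfitting. It gives no z threshold, no rule on direction and no recurrence count that a pattern must reach. It does not mention that the folds' training sets overlap.

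**The concern.** Rediscovery supports a pattern only so far as the second look uses different children. Here the looks come from one partition. A child held out in one trial is a training child in many of the others, so a chance association in one training set is carried into the next by the children they share. This applies to a single pattern and is separate from how many patterns are screened.

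The rules are meant to predict treatment response in new cases and to feed the clinical decision framework of Aim 3. A chance rule labelled stable would enter those discussions with more credit than the data give it.

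**Working it through.** The protocol states no recurrence or stability figure, so there is none to reproduce. The question is how often a noise pattern recurs.

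**Inputs from the protocol.** Ten sets; one for testing per fold; the other nine divided between training and parameter validation; a z-score per pattern.

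**Assumptions, because the protocol is silent.** k = 4 to 8 training sets; |z| > 1.96 (two-sided 0.05); indicator present in one third of children; response 50:50 and unrelated to the indicator; N between 84 and 202. N hardly affects the result.

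**Step 1: overlap.** If training sets are taken in rotation, the average share of children common to two trials is (k − 1)/9. If they are drawn at random from the nine, it is 8k/81.

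- k = 4: 3/9 = 33% or 32/81 = 40%
- k = 6: 5/9 = 56% or 48/81 = 59%
- k = 8: 7/9 = 78% or 64/81 = 79%

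**Step 2: from overlap to recurrence.** For a noise pattern, the correlation ρ between the z-scores of two trials equals the share of children in common. With (Z1, Z2) bivariate normal with correlation ρ,

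P(recurs, same direction) = P(Z1 > 1.96, Z2 > 1.96) / 0.025.

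This gives 2.5% at ρ = 0, 7.9% at 0.25, 18.5% at 0.50 and 38.1% at 0.75. For k = 4 in rotation, a trial shares 3, 2 or 1 of its 4 sets with two other trials each, and none with three. The average is [2 × (38.1 + 18.5 + 7.9) + 3 × 2.5]/9 = 136.5/9 = 15.2%. The same averaging gives 25.1% for k = 6 and 41.8% for k = 8. If all pairs overlapped equally at 33%, the figure would be about 11%, so the lower end also depends on how training sets are chosen.

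**Step 3: simulation with adjusted residuals** (40,000 noise patterns per setting):

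| Training sets | Recurs, same direction | Ratio to 2.5% | Ratio to 5%, direction ignored |
|---|---|---|---|
| 4 | 15% | 15/2.5 = 6 | about 3 |
| 6 | 25% | 25/2.5 = 10 | about 5 |
| 8 | 41-42% | 42/2.5 = 17 | about 8 |
| Disjoint halves | about 2.5% | 1 | 1 |

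At a threshold of 0.01 with eight training sets, the ratio with direction ignored is about 33, so no single multiple can be quoted without its assumptions.

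**Step 4: unconditional rates.** The figures above condition on significance in one trial. Among all noise patterns with eight training sets, about 5% are significant in any given trial, 3.5% in at least 5 of 10, 1.2% in at least 8 and 0.4% in all ten. With six training sets, 0.2-0.3% reach at least 8. If the trials were independent, effectively none would reach 8.

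**Step 5: the held-out check.** Within one fold, a noise pattern found in training is significant in the unseen set in about 5% of cases (4.6% at N = 202, 5.3% at N = 101), with either direction about equally likely. That check is sound. Now take only noise patterns that recur in at least 8 trials (eight training sets) and look across all ten test sets: they keep their direction in 76-83% of them, where 50% would be neutral. The reason is that each test set supplies training children to eight of the other nine folds. Selecting on recurrence has therefore already used the test children.

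**The case against.** The strongest reply is that rediscovery is only part of the procedure. The same text tests discovered patterns on unseen children, and within a fold this works as intended. Overlap is built into every k-fold scheme, the protocol never says the folds are independent, and fold-to-fold stability is a fair description of sensitivity to leaving some children out. A strict recurrence rule also filters noise: at 1.2%, recurrence in at least 8 of 10 is harder for a noise pattern to meet than one 5% test. The split, the threshold and any recurrence cut-off could properly sit in an analysis plan that is not shown.

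Most of this stands, and it rules out several readings that a reader might infer:

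- **That the validation cannot tell real rules from chance rules.** The held-out checks and the 1.2% figure contradict this.
- **That the trials always share most of their children.** This holds with six or more training sets (56% or more) but not with four or five (33-44% in rotation).
- **That one inflation factor follows from the protocol.** It does not; threshold, direction rule and split are all unstated.
- **That rules go to Aim 3 because they recur.** The protocol sets no such rule. It speaks of significant and meaningful rules with attached confidences, which are then reviewed with clinical leaders.

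What the reply does not remove is that the protocol itself names rediscovery as what validates a pattern, and does not require a rule to pass the held-out check. Once patterns are picked for recurring, the pooled test sets no longer give a neutral verdict (Step 5). Missing details could be left to an analysis plan; the stated meaning given to recurrence is already fixed here.

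**Conclusion.** The point holds in a limited form. Raw recurrence across these ten trials is not validation, and without calibration it is weak evidence of stability. With 4 to 8 training sets and a two-sided 0.05 threshold, a noise pattern found once recurs in the same direction in about 15-42% of other trials, against about 2.5% in disjoint data: roughly 6 to 17 times as often, or 3 to 8 times ignoring direction. These figures rest on an assumed split and threshold and should be quoted only with them. The direction of the error does not depend on those choices, because any two trials with shared training children give positively correlated results. The planned held-out checks reduce the problem but do not remove it, as they are neither a condition for keeping a rule nor neutral for rules selected on recurrence.

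**What to change.** Keep the ten-fold procedure and change what recurrence is allowed to mean.

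1. State that recurrence across folds is not validation, and that validity rests on the held-out results, with a stated criterion a rule must meet to be kept.
2. Calibrate stability by permutation: shuffle treatment response across children, rerun the whole procedure including pattern discovery and parameter validation, and record the recurrence counts. Call a rule stable only if its count exceeds a high quantile of that distribution, fixed in advance. This absorbs the overlap whatever split and threshold are used.
3. State the training/validation split, the z threshold and whether recurrence must be in the same direction.

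As an option, stability can be judged on repeated random halves, requiring the rule in the same direction in both halves in a pre-set share of splits. Half-samples find weak true rules less often, so the permutation version is preferable.

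The cost is a change of wording and computing time; no extra data or visits are needed. Fewer rules may earn the label stable.
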